11.6. Adherence Analyses

Treatment adherence based on pill count and on subject self-report will be summarized by means of descriptive statistics and frequency tabulations.

Adherence rates will be reported according to the proportion of subjects taking $>95\%$, $80-95\%$ and $<80\%$ of study drug as assessed by pill count at study visits at Weeks 4, 8, 12, 24, 36, and 48.

11.7. Retention in Care Analyses

Number of subject with retention of care by age, gender, race, sexual orientation, time from diagnosis to baseline visit, baseline CD4+ cell count, baseline HIV-1 RNA, patient satisfaction as assessed by HIVTSQs, and socioeconomic factors will be tabulated.

11.8. Safety Analyses

For all safety endpoints listed in Section 2.1.2, descriptive statistics will be used to summarize the endpoints.

Adverse Events

The verbatim terms used in the eCRF by investigators to identify adverse events will be coded using the Medical Dictionary for Regulatory Activities (MedDRA). Treatment-emergent adverse events are adverse events with onset during the treatment phase or that are a consequence of a pre-existing condition that has worsened since baseline. All reported adverse events will be

included in the analysis. For each adverse event, the percentage of subjects who experience at least 1 occurrence of the given event will be summarized.

Summaries, listings, datasets, or subject narratives may be provided, as appropriate, for those subjects who die, who discontinue treatment due to an adverse event, or who experience a severe or life-threatening (grade 3 or 4) or a serious adverse event.

Additionally, a summary and listing of those subjects meeting predefined stopping rules due to safety or resistance findings will be tabulated.

Clinical Laboratory Tests

Abnormalities will be analyzed according to the DAIDS grading table (see [Attachment 2](#)) and in accordance with the normal ranges of the clinical laboratory. Maximum toxicity grades after baseline will be tabulated, and special attention will be given to subjects who develop grade 3 or grade 4 toxicities.

Laboratory data will be summarized by type of laboratory test. Reference ranges and markedly abnormal results (specified in the Statistical Analysis Plan) will be used in the summary of laboratory data. Descriptive statistics will be calculated for each laboratory analyte at baseline and for observed values and changes from baseline at each scheduled time point. Changes from baseline results will be presented in pre- versus posttreatment cross-tabulations (with classes for below, within, and above normal ranges).

Vital Signs

Descriptive statistics of blood pressure (systolic and diastolic), pulse/heart rate, and body weight and changes from baseline will be summarized at each scheduled time point. The percentage of subjects with values beyond clinically important limits will be summarized. See [Attachment 6](#) for the definitions of vital signs abnormalities.

Physical Examination

Descriptive statistics of changes from baseline will be summarized at each scheduled time point.

Patient-reported Outcomes

Descriptive statistics for absolute values and changes in HIVTSQs scores will be calculated at each timepoint, where applicable.

11.9. Extension Period

For the extension period, descriptive statistics or patient data listings will be provided for adverse events, virologic failure, or resistance.

11.10. Interim Analysis

An interim analysis is planned once all subjects have been assessed for safety at Day 3, and for resistance stopping rules at Week 4.

12. ADVERSE EVENT REPORTING

Timely, accurate, and complete reporting and analysis of safety information from clinical studies are crucial for the protection of subjects, investigators, and the sponsor, and are mandated by regulatory agencies worldwide. The sponsor has established Standard Operating Procedures in conformity with regulatory requirements worldwide to ensure appropriate reporting of safety information; all clinical studies conducted by the sponsor or its affiliates will be conducted in accordance with those procedures.

12.1. Definitions

12.1.1. Adverse Event Definitions and Classifications

Adverse Event

An adverse event is any untoward medical occurrence in a clinical study subject administered a medicinal (investigational or non-investigational) product. An adverse event does not necessarily have a causal relationship with the treatment. An adverse event can therefore be any unfavorable and unintended sign (including an abnormal finding), symptom, or disease temporally associated with the use of a medicinal (investigational or non-investigational) product, whether or not related to that medicinal (investigational or non-investigational) product. (Definition per International Conference on Harmonisation [ICH])

This includes any occurrence that is new in onset or aggravated in severity or frequency from the baseline condition, or abnormal results of diagnostic procedures, including laboratory test abnormalities.

Note: The sponsor collects adverse events starting with the signing of the ICF (refer to Section 12.3.1, All Adverse Events, for time of last adverse event recording).

An adverse event does not include the following:

- Medical or surgical procedures if the condition that leads to the procedure is an adverse event.
- Pre-existing diseases or conditions or laboratory abnormalities present or detected before the screening visit that do not worsen; any medical condition or clinically significant laboratory abnormality with an onset date before the ICF is signed, is not an adverse event. It is considered to be pre-existing and should be documented in the medical history eCRF.
- Situations where no untoward medical occurrence has occurred (eg, hospitalization for elective surgery, social and/or convenience admissions).
- Overdose without clinical sequelae.
- Uncomplicated pregnancy.

See also Section 12.2, Special Reporting Situations and Section 12.3.3, Pregnancy.

Serious Adverse Event

A serious adverse event based on ICH and EU Guidelines on Pharmacovigilance for Medicinal Products for Human Use is any untoward medical occurrence that at any dose:

- Results in death
- Is life-threatening
(The subject was at risk of death at the time of the event. It does not refer to an event that hypothetically might have caused death if it were more severe.)
- Requires inpatient hospitalization or prolongation of existing hospitalization
- Results in persistent or significant disability/incapacity
- Is a congenital anomaly/birth defect
- Is a suspected transmission of any infectious agent via a medicinal product
- Is Medically Important*

*Medical and scientific judgment should be exercised in deciding whether expedited reporting is also appropriate in other situations, such as important medical events that may not be immediately life threatening or result in death or hospitalization but may jeopardize the subject or may require intervention to prevent one of the other outcomes listed in the definition above. These should usually be considered serious. Examples of such events are:

- Intensive treatment in an emergency room or at home for allergic bronchospasm.
- Blood dyscrasias or convulsions that do not result in hospitalization.
- Development of drug dependency or drug abuse.

If a serious and unexpected adverse event occurs for which there is evidence suggesting a causal relationship between the study drug and the event (eg, death from anaphylaxis), the event must be reported as a serious and unexpected suspected adverse reaction even if it is a component of the study endpoint (eg, all-cause mortality).

Additional clarification on adverse events/serious adverse events:

- Complications occurring during hospitalizations are adverse events. If a complication prolongs the hospitalization, it is a serious adverse event.
- In-patient hospitalization means that the subject has been formally admitted to a hospital for medical reasons, for any length of time; this may or may not be overnight. It does not include presentation or care within an emergency department.
- The investigator should attempt to establish the diagnosis of an event on the basis of signs, symptoms, and/or other clinical information; in such cases, the diagnosis must be documented as the adverse event and/or serious adverse event and not the individual signs or symptoms.
- A distinction should be made between seriousness and severity of adverse events. An adverse event that is assessed as grade 4 (potentially life-threatening) should not be confused with a serious adverse event. Severity is a category utilized for rating the intensity of an event, and

both adverse events and serious adverse events can be assessed as grade 4. An adverse event is defined as ‘severe’ when it meets the predefined criteria as described the DAIDS toxicity grading table in [Attachment 2](#) (see also Section 12.1.3, Severity Criteria).

Unlisted (Unexpected) Adverse Event/Reference Safety Information

An adverse event is considered unlisted if the nature or severity is not consistent with the applicable product reference safety information at the time the adverse event is reported. For D/C/F/TAF FDC tablet, the expectedness of an adverse event will be determined by whether or not it is listed in the applicable full Prescribing Information current at the time the event is reported.

Adverse Event Associated With the Use of the Drug

An adverse event is considered associated with the use of the drug if the attribution is possible, probable, or very likely by the definitions listed in Section 12.1.2, Attribution Definitions.

12.1.2. Attribution Definitions

Not Related

An adverse event that is not related to the use of the drug.

Doubtful

An adverse event for which an alternative explanation is more likely, eg, concomitant drug(s), concomitant disease(s), or the relationship in time suggests that a causal relationship is unlikely.

Possible

An adverse event that might be due to the use of the drug. An alternative explanation, eg, concomitant drug(s), concomitant disease(s), is inconclusive. The relationship in time is reasonable; therefore, the causal relationship cannot be excluded.

Probable

An adverse event that might be due to the use of the drug. The relationship in time is suggestive (eg, confirmed by dechallenge). An alternative explanation is less likely, eg, concomitant drug(s), concomitant disease(s).

Very Likely

An adverse event that is listed as a possible adverse reaction and cannot be reasonably explained by an alternative explanation, eg, concomitant drug(s), concomitant disease(s). The relationship in time is very suggestive (eg, it is confirmed by dechallenge and rechallenge).

12.1.3. Severity Criteria

An assessment of severity grade will be made using the general categorical descriptors outlined in the DAIDS toxicity grading table in [Attachment 2](#).

The investigator should use clinical judgment in assessing the severity of events not directly experienced by the subject (eg, laboratory abnormalities).

A distinction should be made between seriousness and severity of adverse events. An adverse event assessed as grade 4 (potentially life-threatening) should not be confused with a serious adverse event. Severity is a category utilized for rating the intensity of an event, and both adverse events and serious adverse events can be assessed as grade 4. An event is defined as ‘serious’ when it meets one of the predefined outcomes listed in Section 12.1.1, Adverse Event Definitions and Classifications.

Clinical Laboratory Abnormalities and Other Abnormal Assessments as Adverse Events or Serious Adverse Events

Laboratory abnormalities are usually not recorded as adverse events or serious adverse events. However, laboratory abnormalities independent of the underlying medical condition that require medical or surgical intervention or lead to study drug interruption or discontinuation must be recorded as an adverse event as well as a serious adverse event, if applicable. Laboratory or other abnormal assessments (eg, vital signs) that are associated with signs and/or symptoms must be recorded as an adverse event or serious adverse event if they meet the definitions as described in Section 12.1.1, Adverse Event Definitions and Classifications. If the laboratory abnormality is part of a syndrome, the syndrome/diagnosis (ie, anemia) must be recorded and not the laboratory result (ie, decreased hemoglobin).

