3. STUDY DESIGN AND RATIONALE

3.1. Overview of Study Design

This is a single-arm, open-label, prospective, multicenter Phase 3 study to assess the efficacy and safety of D/C/F/TAF FDC in newly diagnosed (ie, within 2 weeks of the screening/baseline visit [Day 1]) HIV-1 infected treatment-naïve subjects at least 18 years of age as part of a Test and Treat model of care in the USA.

A target of approximately 100 subjects will participate in this study.

After obtaining informed consent, a blood sample will be collected for central laboratory testing. The in- and exclusion criteria will be reviewed to confirm the subject's eligibility. The screening/baseline visit (Day 1) should take place no later than 2 weeks following evidence of newly documented HIV-1 infection.

Study drug will be dispensed before the results from the screening/baseline safety and resistance laboratory tests are available. Subjects will receive treatment in a single-arm open-label fashion as follows:

- **D/C/F/TAF: DRV 800 mg + COBI 150 mg + FTC 200 mg + TAF 10 mg FDC**

Subjects must start treatment within 24 hours of the screening/baseline visit.

Following initiation of treatment, a safety assessment will be performed by the investigator at Day 3 +1 week, or as soon as the final screening/baseline laboratory report becomes available.

Subjects meeting any of the below safety stopping rules (based on the receipt of the screening/baseline laboratory findings) will be contacted to return to the study site for possible early study treatment discontinuation (ESTD) and for additional follow-up.

- Estimated glomerular filtration rate (eGFR) according to the Modification of Diet in Renal Disease (MDRD^{19,22,33}) formula <50 mL/min.
- Aspartate aminotransferase (AST) or alanine aminotransferase (ALT) $\geq 2.5 \times$ upper limit of normal (ULN)
- Serum lipase $\geq 1.5 \times$ ULN
- Positive serum human chorionic gonadotropin pregnancy test (β -hCG) for women of childbearing potential
- Laboratory results that the investigator believes should result in discontinuation of study medication (Note: It is recommended that the investigator contacts the sponsor's medical monitor to discuss the discontinuation)
- Subjects identified with active hepatitis C virus (HCV) infection that in the opinion of the investigator requires HCV treatment immediately or expected to be needed during the course of the study with agents not compatible with D/C/F/TAF FDC.

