- In case of rash, safety blood samples need to be taken and are to be processed by the central laboratory. For details on rash management, see Section [9.8.2](#), Cutaneous Events/Rash.

Vital Signs (Including Height and Weight)

Blood pressure (systolic and diastolic) and pulse/heart rate measurements (supine after at least 5 minutes rest) should be preceded by at least 5 minutes of rest in a quiet setting without distractions (eg, television, cell phones). Blood pressure and pulse/heart rate measurements will be assessed with a completely automated device. Manual techniques will be used only if an automated device is not available.

To obtain the actual body weight, subjects should be weighed lightly clothed.

Height should be measured barefooted at the screening visit.

Any clinically relevant findings at screening and changes occurring during the study must be recorded in the Adverse Event section of the eCRF.

Physical Examination

Complete physical examinations, or symptom-directed examinations (physical examinations for which symptoms have been reported by the subject) as needed, will take place at the time points in the [Time and Events Schedule](#).

Complete physical examinations include skin, eyes, ears, nose, and throat, head, neck, and thyroid, heart, lung, chest (incl. breasts), abdomen, genitalia, anorectal, lymph nodes, musculoskeletal, and neurological. Urogenital/anorectal examination will be performed at the discretion of the investigator if clinically relevant. Subjects should be undressed during the complete physical examinations, which should be performed by a licensed medical doctor, physician's assistant or nurse practitioner in accordance with local guidelines.

Any clinically relevant findings at screening and changes occurring during the study must be recorded in the Adverse Event section of the eCRF.

Patient-reported Outcomes

Patient-reported outcomes will be assessed at the time points indicated in the [Time and Events Schedule](#) utilizing the HIVTSQs. The HIVTSQs should be completed before all other study-related procedures planned during these visits to prevent influencing subject perceptions.

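### Conflicting rules on where pre-dose findings are recorded, with all reported adverse events analysed, allow one baseline-laboratory stop to count under several safety endpoints

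*Protocol*

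**What the plan says.** **Design.** Under Protocol Section 3.1, study drug is dispensed before the screening/baseline safety results are available. The safety stopping rules are then applied "based on the receipt of the screening/baseline laboratory findings". Section 3.1 speaks of possible early discontinuation, whereas Section 10.2 lists meeting a safety stopping rule among the reasons why treatment must stop.

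**Recording.** Four statements bear on a finding made before the first dose.
- Section 12.1.1: "The sponsor collects adverse events starting with the signing of the ICF". It also says that "any medical condition or clinically significant laboratory abnormality with an onset date before the ICF is signed, is not an adverse event" and assigns such conditions to the medical history page.
- Section 12.1.3: "Laboratory abnormalities are usually not recorded as adverse events or serious adverse events". The exception is for abnormalities independent of the underlying condition that need intervention or that "lead to study drug interruption or discontinuation must be recorded as an adverse event".
- Section 9.7, under Vital Signs and again under Physical Examination: "Any clinically relevant findings at screening and changes occurring during the study must be recorded in the Adverse Event section of the eCRF".
- Section 9.7, under Clinical Laboratory Tests: only clinically relevant changes during the study go to the adverse event page.

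**Analysis.** Section 11.8 defines treatment-emergent events as those with onset in the treatment phase, or arising from a pre-existing condition that has worsened since baseline. It then states that "All reported adverse events will be" included in the analysis and uses that scope for the per-event percentages. The synopsis limits this to onset during the study, which still covers the time before dosing. In Section 2.1.2, safety-stopping-rule discontinuation, discontinuation due to adverse events, and grade 3 and 4 adverse events are separate secondary endpoints. None is limited to treatment-emergent events.

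**The concern.** In most trials a subject with an abnormal screening value is never dosed, so loose wording on pre-dose findings does little harm. Here the design doses such subjects and then stops them, so discontinuations caused by pre-dose values are a foreseeable product of the protocol. The adverse event wording makes no allowance for this.

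Two things are at stake. First, sites may handle the same finding differently: one may enter a Day 1 value on the adverse event page because it led to discontinuation, another in medical history because it presumably began before consent. Second, once such a value is on the adverse event page, nothing in the stated analysis removes it. The adverse-event-discontinuation and grade 3-4 proportions would then mix events on treatment with abnormalities that were present before the first tablet. With about 100 subjects and no control arm, a few such cases can change how tolerability reads. The interim analysis follows the Day 3 and Week 4 reviews, which is when baseline-driven stops fall due.

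**Working it through.** **1. The plan's own adverse event figure.** Section 11.3 gives the probability of seeing at least one event in 100 subjects as 63% and 98% for true incidences of 1% and 4%. The formula is 1 - (1 - p)^100.
- p = 0.01: 1 - 0.99^100 = 0.634.
- p = 0.04: 1 - 0.96^100 = 0.983.

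Both agree with the protocol. They are not in dispute and say nothing about how often baseline values trigger a stop.

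**2. One subject traced through the text.**
- Consent is signed, blood is drawn, and drug is dispensed and started within 24 hours (Section 3.1).
- The result arrives and meets a safety stopping rule (Section 3.1). Treatment is stopped (Section 10.2).
- Section 12.1.3: the abnormality led to discontinuation, so if it is independent of the underlying condition it goes on the adverse event page.
- Section 12.1.1: if onset was before consent, it goes to medical history. But the abnormality was first seen on a sample drawn after consent, so its onset date may be unknown. The exclusion for abnormalities present or detected before the screening visit does not settle the case either.
- Section 11.8: if it was entered as an adverse event, it is analysed.
- Section 2.1.2: the subject counts under the stopping-rule endpoint. If the discontinuation is attributed to that adverse event, the subject also counts under discontinuation due to adverse events.

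**3. Can it also reach the grade 3-4 adverse event endpoint?** The stopping thresholds in Section 3.1 are set against the grading table in Attachment 2.
- eGFR below 50 mL/min: grade 3 covers below 60 down to 30, and grade 4 is below 30. Every subject who meets this rule is grade 3 or worse.
- ALT or AST from 2.5 times ULN: this is where grade 2 starts. Grade 3 starts at 5 times ULN.
- Lipase from 1.5 times ULN: this is where grade 2 starts. Grade 3 starts at 3 times ULN.

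So the eGFR rule always opens the third count, and the other two do so only for higher values. The laboratory tabulation is not affected, because Section 11.8 takes maximum toxicity grades after baseline. The adverse event summaries have no matching limit.

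**4. Scale (assumption only).** The protocol gives no proportion of subjects expected to meet a baseline stopping rule. For scale, take the 2.3% discontinuation for adverse drug reactions that Section 1.2.1 cites for darunavir/ritonavir in treatment-naive adults. Let s be an assumed percentage stopped on baseline laboratory values and, as a worst case, suppose that all are coded as adverse event discontinuations. The reported proportion is 2.3% + s, and the pre-dose share is s / (2.3% + s).

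| s | Reported | Pre-dose share | Chance of at least one in 100 |
|---|---|---|---|
| 1% | 3.3% | 30% | 63% |
| 2% | 4.3% | 47% | 87% |
| 5% | 7.3% | 68% | 99% |
| 10% | 12.3% | 81% | above 99.9% |

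The last column is the formula from step 1 with p = s.

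**The case against.** The case for leaving the text alone has weight.

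- **The protocol does not uniformly require it.** A reader might infer that every pre-dose laboratory abnormality must be recorded as an adverse event. That is not supported: Section 12.1.1 excludes onset before consent, and Section 12.1.3 begins from the position that laboratory abnormalities are usually not recorded. Screening and baseline must be completed within 2 business days of consent (Section 4), so most Day 1 abnormalities will in truth have begun earlier. This stands, and it reduces the point to a contradiction that permits miscounting. It does not remove the point, because onset is undocumented at first detection and Section 12.1.3 has no pre-dose exception.
- **The screening sentence in Section 9.7 is not about laboratory values.** This stands. It appears only under vital signs and physical examination. It can add screening findings to the adverse event counts, but it does not itself produce the double count of laboratory stops.
- **Attribution is recorded separately.** A reader might infer that the rate attributed to the drug is inflated. Section 12.3.1 has the investigator record relatedness for each event, and the endpoint is discontinuation for adverse events of any cause. The documents support mixing of pre-dose and on-treatment findings, not false attribution.
- **Overlap of endpoints is not in itself an error.** Correct; Section 2.1.2 does not declare them exclusive. The difficulty is that the overlap would depend on which recording rule a site follows.
- **The SAP may restrict the tables.** It was not available here and may do so. But Section 11.8 itself states a scope wider than treatment-emergent events, and no analysis plan can make inconsistent site recording consistent afterwards.

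**Conclusion.** The point holds as a conflict between recording instructions, combined with a stated analysis scope that does not screen out the result. A subject stopped on a pre-dose laboratory value can be counted under the stopping-rule endpoint and under discontinuation due to adverse events. For eGFR below 50 mL/min the grade 3-4 adverse event endpoint is open as well. Clinically relevant screening examination and vital-sign findings can enter the general adverse event counts.

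The size cannot be derived from the documents. The table above rests on an assumed rate of baseline stops, on complete coding of those stops as adverse events, and on a 2.3% figure that comes from another regimen, covers drug reactions only and runs to 192 weeks. A reader might take the resulting ratios as an estimate of bias in this trial; they only restate the assumptions. The change is worth making because it is cheap and the design makes such stops foreseeable.

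**What to change.** 1. **Section 11.8 and the synopsis:** base the adverse event summaries, the adverse-event-discontinuation endpoint and the grade 3-4 adverse event endpoint on treatment-emergent events as already defined. List events between consent and first dose separately. Use the same scope sentence in both places.
2. **Endpoints:** report discontinuations driven by screening/baseline laboratory values under the stopping-rule endpoint only.
3. **Sections 9.7, 12.1.1 and 12.1.3:** reconcile them so that abnormalities found on pre-dose samples or examinations are recorded as baseline or medical history unless they worsen. Key the rule to the sample or examination being pre-dose, since Day 1 blood and the first dose can share a date. Do not send everything found at screening to medical history: new events arising after consent, such as those caused by a study procedure, must still be collected as adverse events.
4. **Sections 3.1 and 10.2:** reconcile the possible discontinuation in the first with the mandatory one in the second. Which is right is a clinical decision and is not argued here.

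The cost is wording in these sections and matching eCRF completion guidance. The treatment-emergent definition already exists, and no new data or visits are needed. If sites have begun entering data, adverse event entries that rest on pre-dose findings should be checked once against the reconciled rule.
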